1.3 HYPOTHESES OF RESEARCH

- H0: There is no difference on functional outcomes on functional otucomes after TKA in patients that received preoperative information and those who did not.
- H1: There is difference on functional outcomes on functional otucomes after TKA in patients that received preoperative information and those who did not

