3.2 PARTICIPANTS

Sample size estimation calculations were performed taking into consideration the primary outcome measure - Timed up and Go (TUG) test score. These calculations were based on the study published by Mizner et al (2005), and considering a Minimal Clinically Important Change of 2,27 seconds in the TUG score (Yuksel et al, 2016). Considering a power of 80% and a two-sided 0.05 significance level, 28 patients would be necessary to detect a 2.27 second difference between the two arms (14 patients in each arm). Considering a dropout rate of 10%, the total sample size would be 31 patients. We have decided to extend the sample size to 40 patients (20 patients in each arm), assuming small variations on the baseline TUG scores and standard deviation in the study population..

The sample will be recruited between patients of both sexes with indication for total unilateral knee arthroplasty in the city of Florianópolis and referred by orthopedic physicians. The collection will take place in the period between July 2017 and April 2018. Participants will be divided into two groups of equal size: intervention group (GI) who will receive preoperative oral guidance and a leaflet with information related to their physical condition as well as signs and symptoms in the postoperative period (APPENDIX A); Control group (GC) who will receive only verbal guidance in the preoperative period.

The evaluations will occur in three moments (preoperative, 6 weeks and 6 months after the arthroplasty). On the day of the first collection, the participants will be allocated to each group according to the draw made by a team member who will not participate in the evaluations. This same member will deliver the package leaflet to the GI participants. Evaluators will be blinded to individuals participating in IG and GC. All participants will receive information about the objectives and procedures of the study through the Informed Consent Form (APPENDIX B) prior to the collection.

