3.2.1 Inclusion and exclusion criteria

The following criteria will be used:

Inclusion:

- Age above 55 years;

- Literate;

Elective submission of total unilateral knee arthroplasty (TKA) due to osteoarthrosis;
Que não tenham realizado substituição unicompartimental anterior ou osteotomia de tíbia no mesmo joelho;

- Who have not had knee infection or other serious complications after TKA;

- Body mass index less than 40 kg / m2;

- That he has not performed other arthroplasties on the lower limb in the last 6 months;

- Movement arc greater than 90° in the operated or contralateral knee.

Exclusion

- Associated condition that impedes performance in gait tests, including significant osteoarthrosis in the contralateral knee or hips (defined as pain greater than or equal to 5 in VAS);

- Absence or abandonment in the study follow-up sessions.

Blinding

The nature of the study will allow blinding of the patients regarding study arms. Participants will be blinded to the primary and secondary outcomes being measured. Baseline patient assessment, as well as outcomes assessment at 6 weeks and 6 months will be performed by one investigator blinded for experimental or active comparator arms. Statistical analysis will be performed blinded for experimental or active comparator arms. Patient assessment

Patients will be assessed at baseline (pre-operatively), in 6 weeks after surgery and 6 months fter surgery.

Baseline assessment

Participant characterization will consist of:

- a) Demographics (gender, date of birth);
- b) Educational level (years);
- c) Diagnosis
- d) Affected side
- e) Date of surgery
- f) Gait analysis
- g) Timed Up and Go test
- h) Knee Osteoarthritis Score WOMAC
- i) EMG muscle activity
- j) Kinesiophobia
- 1) Postural control

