## STATISTICAL ANALYSIS PLAN

Descriptive statistics (mean, standard deviation) will be used to describe the participants involved and results of kinesiophobia cover scale, WOMAC scale, gait analysis and TUG. The spatiotemporal and kinetic parameters, electromyographic activation, TUG and postural control will be analyzed by analysis of variance 3x2 considering time factor (pre, post 6 weeks, post 6 months) and groups (with and without informative leaflet), respectively. If the sphericity hypothesis is rejected, the Huynh-Fedt correction will be applied. Effect sizes will be computed by means of partial square eta values. The SPSS 20.0 package will be used for all analyzes. The p value used will be 0.05.

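### TUG is named primary in the protocol, but neither H1 nor the SAP ties the leaflet claim to TUG or to one test, so the error rate of that claim is not fixed at 5%

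*SAP*

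**What the plan says.** - **Sample size (Protocol, Section 3.2).** The calculation rests on "the primary outcome measure - Timed up and Go (TUG) test score" and a difference of 2.27 s between the two arms: "Considering a power of 80% and a two-sided 0.05 significance level, 28 patients would be necessary". The total becomes 31 with 10% dropout and is then set at 40.
- **Blinding (Protocol, Section 3.2.1).** "Participants will be blinded to the primary and secondary outcomes being measured". Two classes of outcome are recognised here, but the secondary ones are not listed.
- **Hypotheses (Protocol, Section 1.3).** H1 reads "There is difference on functional outcomes on functional otucomes after TKA", comparing patients with and without the preoperative information. No outcome, visit or effect is named.
- **Aims elsewhere in the protocol.** The abstract spans gait, functional mobility, postural control and kinesiophobia. Section 1.1 ends on gait recovery and kinesiophobia. Section 3.8 hopes to confirm a benefit on kinesiophobia and functionality.
- **SAP.** "The spatiotemporal and kinetic parameters, electromyographic activation, TUG and postural control will be analyzed by analysis of variance 3x2", with visit (three levels) and group (two levels) as factors. The level is set once: "The p value used will be 0.05". The SAP gives no primary outcome, order of testing or multiplicity rule, and does not say which ANOVA effect answers the question. WOMAC and kinesiophobia appear only under descriptive statistics.

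**The concern.** The trial is sized for one comparison of one outcome, and 0.05 is the error rate of that comparison. The SAP does not identify it. TUG sits in the middle of a list, and every item on the list gets the same ANOVA at the same level. Each ANOVA yields a group effect and a group-by-time effect, either of which could be read as the leaflet effect.

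With H1 worded for functional outcomes in general, a later report could present a significant gait or balance result, or whichever TUG effect reached 0.05, as confirming H1 without departing from the plan. At stake is whether a positive claim for the leaflet carries the 5% error rate that the documents imply.

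**Working it through.** **1. The plan's own figure.** Section 3.2 gives 28 patients (14 per arm) for 2.27 s at 80% power and two-sided 0.05, but no numerical SD, so 28 cannot be reproduced independently. Solving backwards with the normal formula:

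SD = 2.27 / [(1.960 + 0.842) × √(2/14)] = 2.14 s (2.06 s with the t distribution).

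For assumed SDs of 2.0, 2.5 and 3.0 s, the number per arm is 13, 20 and 28. The dropout step agrees: 28 × 1.1 = 30.8, so 31. What matters here is the form of the calculation: one outcome, one two-arm difference, one test at 0.05, with no allowance for other tests.

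**2. Number of outcomes sent to the ANOVA.** Neither document states a number. This count comes from Section 3.5.3 (muscles) and the data-processing paragraphs after Section 3.5.5.

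| Group | Count |
|---|---|
| Step length, stride length, symmetry, step time, single support, double support, adductor moment | 7 |
| Coefficient of variation of step duration | 1 |
| EMG muscles | 4 |
| TUG | 1 |
| Centre-of-gravity velocity (one summary, or six conditions) | 1 to 6 |
| Centre-of-pressure displacement and velocity, two directions each | 4 |
| **Total, TUG included** | **18 to 23** |

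The total is 19 to 24 if the step-time item means step time and stride time separately.

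**3. Chance of at least one p < 0.05 when the leaflet has no effect on anything.** With independent outcomes and one effect per outcome, this is 1 − 0.95^m:

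- m = 18: 1 − 0.95^18 = 0.603
- m = 23: 1 − 0.95^23 = 0.693

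The outcomes are likely to be correlated, so the 3x2 mixed ANOVA was also simulated: 20 per arm, no true effects, equal correlation between all outcomes, within-subject correlation 0.5 (assumed), 4,000 runs per setting.

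| Correlation between outcomes | Interaction only, 18 outcomes | Interaction only, 23 outcomes | Either effect, 18 outcomes | Either effect, 23 outcomes |
|---|---|---|---|---|
| 0 | 61% | 69% | 85% | 91% |
| 0.3 | 50% | 59% | 76% | 84% |
| 0.5 | 41% | 46% | 66% | 71% |
| 0.7 | 29% | 33% | 49% | 52% |
| 0.9 | 16% | 17% | 29% | 31% |

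Counting one effect per outcome, the range is about 16% to 69%.

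**4. TUG alone.** One named effect gives 5%. If either the group or the group-by-time effect counts, 1 − 0.95² = 0.0975 (simulated 9.9%).

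**5. Whether either ANOVA effect matches Section 3.2.** The group main effect averages all three visits, including the preoperative one that the protocol uses as baseline. If the leaflet changed TUG by 2.27 s at both post-operative visits and by nothing at baseline, the main effect would estimate (0 + 2.27 + 2.27)/3 = 1.51 s, and it would carry any chance baseline imbalance. The group-by-time effect compares profiles over three visits on 2 degrees of freedom. It is not a two-arm difference of 2.27 s at a stated visit. So neither effect is the contrast that was sized.

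**The case against.** The SAP should be read with the protocol. Section 3.2 names TUG as primary and sizes the trial on it alone, and Section 3.2.1 separates primary from secondary outcomes. A reader might infer from the SAP that the trial has no primary outcome, or that any significant result establishes H1, so that the false-claim rate simply is 60% to 69%. The documents do not support either inference. A primary outcome is named, and no sentence says that any single significant outcome suffices. This part of the objection stands: the inflated figures are conditional on a rule that the documents neither state nor exclude.

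It can also be said that EMG amplitudes and centre-of-pressure measures are not functional outcomes. The paragraph closing Section 3.5.5 lists gait parameters, postural control and functionality separately. Sections 3.3.6 and 3.3.8 attach function to WOMAC and TUG, and the SAP only describes WOMAC. On that reading TUG is the only tested measure of function. The reading is possible, but the title, objective and abstract are broader and H1 does not choose. Even on the narrow reading, two effects and two post-operative visits remain open for TUG.

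The count is approximate. It multiplies sway velocity by six conditions but counts the centre-of-pressure measures once, and it leaves out the knee flexion angle defined in Section 3.3.4. Different choices would mostly raise it. Finally, several measures are closely related, so independence gives the top of the single-effect range. That is correct, and it is why a range is given.

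**Conclusion.** The point holds in a conditional form. The protocol's primary outcome is not carried into H1 or the SAP, and no single test of the leaflet is named, so the plan does not fix the error rate of the claim it is set up to make.

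- If any listed outcome may support H1, the rate is about 16% to 69% with one effect counted per outcome. This assumes 18 to 23 outcomes, no true effects, and correlations between outcomes from 0.9 down to 0.
- If H1 is judged on TUG but either ANOVA effect counts, it is about 9.75%.
- If H1 is judged on TUG by one named test, it is 5%, and the other outcomes are ordinary secondary outcomes.

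This is more than missing detail, because it decides what the trial may claim. It is not evidence that the sponsor intends to claim H1 from any outcome.

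**What to change.** 1. Restate H0 and H1 for TUG, comparing leaflet plus verbal guidance with verbal guidance alone.
2. State in the SAP that TUG is the only confirmatory outcome, tested once at two-sided 0.05.
3. Name one between-arm comparison that matches the 2.27 s difference in Section 3.2, for example the baseline-adjusted arm difference at one post-operative visit chosen in advance by the sponsor. If the ANOVA is kept for the primary test, name the group-by-time effect and acknowledge that it is a 2-df test that does not match the sample size contrast.
4. State that the group and time main effects are not evidence for the leaflet.
5. Label all other outcomes secondary or exploratory and report them as arm differences with 95% confidence intervals, not as confirming H1. Banning every p-value for them would be a matter of preference and is not needed.

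The cost is wording in the hypotheses and the SAP. Sample size, visits and measurements do not change. The downside is that a significant secondary outcome can no longer be presented as confirming H1.
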